D.3.1. Sample. A total of 536 participants will be recruited and randomized to either the BMI+SC or SC condition during the first four and a half years of the study. The proposed sample size is feasible based preliminary data (i.e., approximately one eligible participant per recruiting day). We will screen approximately 545 participants per year (in 1:1 format). Based on preliminary data, 22% of these participants ($n=119$) will meet eligibility criteria for the study. We estimate attrition during follow-up at approximately 25% based upon Preliminary Study 2, leaving approximately 91 participants per year (or a total of 416 across 4.5 years) for analysis.

D.3.2. Rationale for standard care control group. Ultimately it is important to determine whether the BMI is efficacious relative to a specific active comparison condition. However, it is first necessary to determine whether the BMI+SC works at all compared to SC, taking into account affective psychopathy scores. Approximately 50% of all MCPS clients are mandated through the court system to complete substance abuse treatment, though the number who do so is lower. For the proposed study, the SC condition will include individuals who receive levels of non-study intervention that vary widely, from none to substantial. This real world condition provides the potential for useful generalization of results to other supervision programs, and is an appropriate comparison for assessing a brief intervention that may best serve as an adjunct to SC. The SC condition will consist of no research-related intervention beyond the baseline assessment session, but we will measure and analyze all non-study treatment participation carefully. Individuals in MCPS do not receive substance use services onsite, though some are referred to community providers for treatment. For anyone involved in non-study treatment, we will measure number of sessions and type of treatment in order to ensure that comparisons between BMI+SC and SC take into account all extra-study treatment.

D.4. Overview of Study Appointments

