**Brief Intervention for Justice-Involved Substance Users:
Harnessing Mechanisms of Change**

NCT03308877

04/01/2017

D.7. Data Analysis. A baseline check of randomness will be conducted for each variable collected. Categorical variables will be analyzed using chi-square tests; continuous variables with ANOVAs. To assess Hypothesis 1 continuous outcomes, Analysis of Covariance will be used. The effects of BMI+SC on commitment to change, self-regulation, and substance use will be assessed immediately following intervention. Longer term substance use effects will be examined at 6-month follow-up. For substance use toxicology results, logistic regression will be used. In all instances, alpha = .05; covariates will include gender, race, age, and the outcome baseline score of interest as well as any other variables found to differ at baseline. Additionally, effect sizes will be examined using marginal means.⁷¹ Structural equation modeling (SEM) will be used to test the hypothesis that the effect of BMI+SC on substance use will be mediated by increases in commitment to change and self-regulation (Figure 2).⁷² *Substance use status* at six month follow-up is the key outcome of interest. We hypothesize that effects on six month substance use are mediated, in part, by BMI+SC effects on commitment to change and self-regulation. Substance use status will be measured using two indicators, percent days abstinent and the urine screen result. *Commitment to Change* will be measured using two indicators at each time point, the Readiness Ruler and the CLEAR change talk score at both baseline and immediate post. Two indicators will also be used to assess *Self-Regulation* at baseline and immediate post: Self-Regulation Questionnaire scores and Balloon Analog Risk Task scores. Additionally, demographic variables will be statistically controlled for in the model (gender, age, race, ethnicity). The MPLUS statistical package⁷³ will be used for SEMs. To provide a metric for each latent construct and to identify the model, the first construct loading for each latent variable will be set at 1.0. A two-step approach examining the model will be undertaken.⁷⁴ First, using confirmatory factor analytic techniques, a test of the proposed measurement model will be conducted and any needed modifications to this model, including testing for measurement invariance over time, will be undertaken prior to examining model fit. The second step involves an examination of the structural portion of the model. The model suggests that BMI effects on substance use are not only direct, but also indirect, mediated by effects on commitment to change and self-regulation. Baseline substance use status, commitment to change, and self-regulation will be controlled for, aiding precision in detecting treatment effects. Fit of the model will be assessed using a chi-square statistic, as well as the more approximate fit indices of the root mean square error of approximation (RMSEA),⁷⁵ the comparative fit index (CFI),⁷⁶ and the standardized root mean square residual (SRMR). Using various cutoffs for fit assessment helps to minimize Type I and Type II errors.⁷⁷ Recommendations that adequate fitting models have $CFI > .95$, $RMSEA < .06$, and $SRMR < .08$ will be adopted here. BMI indirect effects on 6 month substance use will be tested using the bias-corrected confidence limits.⁷⁸ Significance will be assessed by whether or not the 95% confidence limits contain zero. The bias corrected approach has been shown to provide the most accurate confidence limits and greatest statistical power when compared with other existing approaches for detecting mediation.⁷⁸ Multi-group structural equation modeling will be used to test moderated mediation. Two groups (high vs. low/moderate on affective psychopathy) will be compared. We will isolate differences across models by first examining if measurement parameters are equal across groups. Model differences across groups will be tested using the chi-square difference test. Next, we will test for structural differences across groups, examining regression parameter estimates for equality, followed by an examination of latent variables' variances and means across the groups. Such moderated-mediation will allow for isolation of BMI effects on latent variable means, controlling for process differences across the groups. Four exploratory analyses will also be conducted. The first will examine longitudinal change in substance abuse using growth curve analyses. Substance use is measured at baseline, 4 times during the intervention period, and at 6-month follow-up (6 time points). Time will be modeled so that the intercept reflects baseline status and subsequent time points will be modeled as weeks from baseline. Both linear and curvilinear (quadratic) change

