D.7.1 Power, Missing Data, and Type 1 Error Protection. For analyses involving continuous mean differences Optimal Design software was used to assess statistical power. With a sample size of 416, we are adequately powered ($> .80$) to detect a small standardized effect with baseline covariates explaining 40% of the outcome variance (n required = 265 to achieve .80 power). Should baseline covariates explain only 30% of the variance, we are powered at .78 to detect small effects. The inclusion of baseline covariates typically improves precision (at the cost of degrees of freedom)⁷⁹ For the logistic analyses predicting urine screen substance use results and 12-month recidivism, power analyses were conducted using the Stata statistical software program. We are interested in the power of treatment status to significantly detect a difference in positive urine screens and violent recidivism by 12 months. In a likely scenario of 50% positive urine screens, we are adequately powered (.80) to detect a 14% or more difference in rates. Power improves slightly as the baseline rates drift away from 50%. Typical 12-month violent recidivism rates are 20%. Here, we are adequately powered to detect a 12% point difference in rates, even if average absolute baseline covariate correlation with treatment is .3. For the structural equation model to be tested,⁸⁰ our approach allows for the testing of a null hypothesis of not good fit, reversing the role of the null hypothesis in conventional tests of model fit, so that a significant result provides strong support for good fit. With an expected sample size of 416, adequate power ($> .95$) to reject an hypothesis of close fit ($RMSEA > .08$) with 94 degrees of freedom (df) given a population $RMSEA$ of .05 was obtained (proposed model including age, gender, 2 race variable = 94 df). Additionally, adequate power (.99) to reject a hypothesis of not-close fit was obtained. Here, if model fit is extremely good ($RMSEA < .01$), and we test the hypothesis that fit is not close, we have greater than .95 power to reject the null hypothesis that $RMSEA > .05$. Even if sample size drops to 300, power for both the hypothesis of close fit and the hypothesis of not close fit remains above .90. As more degrees of freedom are introduced with the addition of multi-group modeling (psychopathy, gender, race), power improves on the above estimates. For analyses examining mean and rate differences, pairwise deletion of missing data will be used, thus retaining all available information. As a form of sensitivity analysis, however, multiple imputation of missing data will be conducted, which has consistently demonstrated less biased parameter estimates than most other approaches to the handling of missing data.⁸¹ To help control for Type 1 error, the Benjamini-Hochberg (BH) method⁸² will be used to adjust for the multiple comparisons proposed. The BH method adjusts for multiple comparisons by controlling the false discovery rate instead of family-wise error rate. It is less conservative than the more traditional Bonferroni methods, yet still provides adequate protection against Type 1 error.

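### The two power figures for continuous outcomes conflict: 265 needed at R² = .40 implies power of about .90, not .78, at 416 with R² = .30

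*SAP*

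**What the plan says.** SAP D.7.1 holds the only power statement for the continuous outcomes. These include percent days abstinent at 6 months, the proximal outcome in Protocol D.3. The software is named: "For analyses involving continuous mean differences Optimal Design software was used to assess statistical power". The power statement begins "With a sample size of 416, we are adequately powered", gives the power as above .80, and continues "to detect a small standardized effect with baseline covariates explaining 40% of the outcome variance (n required = 265 to achieve .80 power". The next sentence lowers the covariate R²: "Should baseline covariates explain only 30% of the variance, we are powered at .78 to detect small effects".

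SAP D.7 gives the analysis ("To assess Hypothesis 1 continuous outcomes, Analysis of Covariance will be used") and the significance level ("In all instances, alpha = .05"). Neither section gives a numerical effect size or says whether these tests are one- or two-sided.

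The 416 comes from Protocol D.3.1: "A total of 536 participants will be recruited and randomized", and "We estimate attrition during follow-up at approximately 25% based upon Preliminary Study 2".

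**The concern.** The first sentence puts 416 far above the stated requirement of 265. The second puts the same 416 below .80 power after R² drops by ten percentage points. That drop is too small to use up a margin of 416 − 265 = 151 participants, so at least one figure looks wrong.

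What is at stake is what the trial can detect. The two figures imply different effects, and they imply different margins over the requirement: about 150 participants or about 40. With no effect size or sidedness stated, a reader cannot choose between them.

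**Working it through.** **Inputs.** From SAP D.7.1: N = 416; 265 required for .80 power at R² = .40; power .78 at R² = .30. From SAP D.7: alpha .05 and ANCOVA. From Protocol D.3: 1:1 allocation in matched pairs. Effect size d and sidedness are not stated, so d is solved from the plan's own figures and both sidednesses are tried.

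**Formula.** With standardised effect d and total sample N, the standard error of the adjusted difference is √(4(1 − R²)/N). Power ≈ Φ(d/SE − z_α), and required N = 4(1 − R²)(z_α + z_power)²/d². The hand figures below use this normal approximation, with z_α = 1.960 two-sided or 1.645 one-sided. A noncentral t calculation was also run. It gives almost the same powers, and they are insensitive to the number of covariate degrees of freedom.

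**Can one effect size reproduce both figures?** Trying conventional values, as assumptions:

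| d | Sides | N for .80 at R² = .40 (stated 265) | Power at 416, R² = .30 (stated .78) |
|---|---|---|---|
| .20 | two | 472 | .68 |
| .20 | one | 372 | .79 |
| .25 | two | 302 | .86 |
| .25 | one | 238 | .92 |

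One-sided d = .20 comes close to .78 (.785 by noncentral t) but not to 265. No row gives both.

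**Carrying 265 forward (d cancels).**
- N for .80 at R² = .30 is 265 × .70/.60 = 309. Since 416 > 309, power at 416 must exceed .80.
- Two-sided: d = (1.960 + 0.842) × √(2.4/265) = .267. At 416 and R² = .30, SE = √(2.8/416) = .0820, so power = Φ(.267/.0820 − 1.960) ≈ .90 (noncentral t .902).
- One-sided: d = .237, power .89 (noncentral t .893).

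**Carrying .78 back.**
- Two-sided: N for .80 at R² = .40 is 416 × (.60/.70) × [(1.960 + 0.842)/(1.960 + 0.772)]² ≈ 375, or 376 with equal arms. The implied d is about .225.
- One-sided: 378, with d about .199.
- Under these effects, 265 at R² = .40 would give power of only .65 to .67.

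**Readings that might reconcile the figures.**
- Rounding, all in the plan's favour (.80 as .795, 40% as 44.9%, 30% as 25%): power at 416 is still .849 two-sided or .843 one-sided.
- 265 per arm (530 in total): power at 416 with R² = .40 is .70 to .71, against the stated value above .80.
- 402 analysed and not 416: .89 or .88.
- The second figure evaluated at N = 265: .74.
- 265 one-sided and .78 two-sided: .82.
- N = 300 at R² = .30: about .79, but D.7.1 uses 300 only for the model-fit tests.
- 416 with no covariates: .777 two-sided or .780 one-sided. This matches .78 but contradicts the stated 30%.

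**Does the claim of more than .80 at R² = .40 survive?** Under the effect implied by 265, power at 416 is .94 two-sided or .93 one-sided. Under the effect implied by .78, it is .84 or .83. It survives either way.

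**The case against.** The strongest reply is that the conflict assumes one effect size and one N for both sentences. Neither sentence gives a number for the effect, and the second does not repeat N. The two-sided values implied, .268 and .225, could both be called small. That is literally true, but the second sentence is framed as a change in R² alone. If the effect or the sample also changed, the comparison would tell the reader nothing.

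A second reply is that the consequence is small. This largely stands. The expected 416 exceeds 265, 309 and 376 to 378, so no correction forces more recruitment, and the power claim at R² = .40 holds under either figure. This is a correction to the power statement and does not show that the trial is underpowered.

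A third reply is that ANCOVA is normally tested two-sided and that d = .20 appears nowhere in the documents. Both points are fair. The one-sided results are given only because sidedness is not stated, and the conflict is the same either way. The possible origins of the error (a one-sided d = .20 behind .78, or .78 taken from a run without covariates) are conjecture and cannot be checked from the documents.

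**Conclusion.** The concern holds. Reading both sentences at one effect size and N = 416, at least one of 265 and .78 is wrong as written. If 265 is right, .78 should be about .90 two-sided or .89 one-sided, and the plan understates its power. If .78 is right, 265 should be about 376 or 378, and the plan understates the required n by about 110. The documents do not show which.

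The result rests on 1:1 allocation, alpha .05 and an ANCOVA residual variance of 1 − R². It does not depend on the effect size or the sidedness.

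One conditional remark: if the tests are two-sided and the intended d is below about .21, the claim of more than .80 at 416 and R² = .40 fails. At an assumed d = .20, power is .75 at R² = .40 and .68 at R² = .30. Stating d and sidedness would settle this.

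**What to change.** In SAP D.7.1, check 265 and .78 against the Optimal Design output, state the numerical d and the sidedness used, and report one consistent set:

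- If 265 stands: n of 309 for .80 power at R² = .30, and power at 416 of about .90 (two-sided) or .89 (one-sided).
- If .78 stands: n of about 376 (two-sided) or 378 (one-sided) for .80 power at R² = .40.

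A minor related line in Protocol D.3.1: 536 × .75 = 402, and 119 × .75 = 89 per year, not 416 and 91. Either use 402 or state the attrition that 416 implies, 1 − 416/536 = 22.4%. The difference costs about 1 to 1.5 points of power and does not explain the conflict. If the tests are two-sided, 402 analysed gives .80 power for d of about .22 at R² = .40 or .23 at R² = .30, which would be a useful statement of what the trial can detect.

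The cost is a check or re-run of the power software and a few words in D.7.1 and D.3.1. Recruitment, allocation and analysis do not change.

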enhance the efficacy of the intervention and perhaps broaden its therapeutic effects to more participants. This update involves dropping the use of a decisional balance exercise in order to decrease the amount of time spent talking about positive drug use experiences – a practice that may be detrimental and may elicit cravings.^{63,64} Our BMI manual (Appendix B) includes the following steps: establishing rapport, asking permission to discuss drugs and providing feedback regarding the drug use assessment, exploring personal consequences of drug use, eliciting the gap between real and desired quality of life, and discussing readiness to change. The therapist then negotiates a written action plan, during which the participant is supported with empathy, verbal reinforcement, information about drug abuse and treatment providers, and a referral for treatment.¹⁵ Continuing care is important for substance users⁶⁵ and data show that having more than one BMI session significantly enhances outcomes,⁶⁶ thus we will include brief (20-30 minutes), flexible, follow-up intervention sessions (Weeks 2, 4, and 6). Each follow-up session will be preceded by an assessment of substance use since the last session by personnel who are blind to psychopathy and treatment status. The Week 6 follow-up will also include readministrations of the BART and Self-Regulation Questionnaire (mediators) to assess change in self-regulation since baseline. Individuals in the BMI+SC and SC conditions will receive the same number of assessments and the same compensation (\$50) for assessment time. Individuals in both the BMI+SC and SC conditions will be assessed for substance use and treatment contacts at Weeks 2,4 and 6 and again at 6 months.

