D.5.1. Objective measures. Due to the potential for underreporting of substance use, we will obtain breathalyzer and urinalysis drug screen results at each follow-up using Varian Testcup Pro 5, which provides results for THC, methamphetamines, cocaine, benzodiazepines, and morphine. Results will be used to provide an objective measure of substance use to be incorporated in a secondary analysis. For the assessment of recidivism, The New York State Division of Criminal Justice Services (DCJS) maintains a database of criminal charges and convictions across the state. We will contract with DCJS to provide data at 12 months following the intervention or baseline assessment. Additionally, MCPS maintains a database of county-wide charges and convictions. Because each database does not always capture all official charges and convictions, they will be combined for maximum sensitivity (as in Preliminary Study 1). Criminal charges will be used as the primary measure of recidivism. Finally, recent involvement in non-study interventions will be assessed at baseline as a potential confound, and during follow up for descriptive purposes. Based on the results of the primary analyses, this data may also be used in exploratory analyses to determine whether BMI+SC increased substance abuse services utilization. The Coordinated Care Services, Inc. (CCSI) database will provide a novel way to gain objective information about participant treatment contacts—including substance abuse treatment—during the follow-up period. This health surveillance database is maintained by the Monroe County Office of Mental Health and was utilized in Preliminary Study 1. This database is used to track county-wide service contacts, enabling us to obtain services use data even for individuals who are lost to follow up. Moreover, we are able to cross-reference the objective database with our self-report

measure of non-study treatment for increased sensitivity and to check the validity of self-report treatment data.

D.5.2. Assessing Mediators. We will conduct a thorough, multi-method assessment of commitment to

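### The 6-month abstinence ANCOVA omits everyone without a 6-month value and any interim data held for them, and the back-up imputation names no variables

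*SAP*

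**What the plan says.** - **Main rule (SAP D.7.1):** "For analyses examining mean and rate differences, pairwise deletion of missing data will be used, thus retaining all available information".
- **Back-up (SAP D.7.1):** as a sensitivity analysis, "multiple imputation of missing data will be conducted, which has consistently demonstrated less biased parameter estimates than most other approaches". No imputation variables, model or missingness assumption are given.
- **Outcome models (SAP D.7):** ANCOVA for continuous outcomes and logistic regression for toxicology. On timing, "Longer term substance use effects will be examined at 6-month follow-up". On adjustment, "covariates will include gender, race, age, and the outcome baseline score of interest", plus variables found to differ at baseline.
- **Expected loss (Protocol D.3.1):** 536 randomised and 416 for analysis; "We estimate attrition during follow-up at approximately 25% based upon Preliminary Study 2".
- **Interim data (Protocol D.4.4 and D.5.1):** participants in both arms "will be assessed for substance use and treatment contacts at Weeks 2,4 and 6 and again at 6 months", and "we will obtain breathalyzer and urinalysis drug screen results at each follow-up". D.5.1 adds that a county database gives service use even for people lost to follow-up.

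**The concern.** Pairwise deletion retains more than listwise deletion when several outcomes are analysed together, because each analysis keeps everyone who has that outcome. In a model with a single 6-month outcome and baseline covariates it offers no such gain: a participant without the 6-month value leaves the analysis. That participant may have reported use and given urine at Weeks 2, 4 and 6, and the model uses none of it. The claim that all available information is retained therefore fails for this model.

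Percent days abstinent at 6 months is the named proximal outcome (Protocol D.3). If dropout depends on early substance use, and does so differently by arm, the complete-case comparison is biased even though data that could reduce the bias have been collected. The planned imputation may or may not reveal this, depending on variables the SAP does not name. If it used only the covariates listed for the outcome models, it would agree with the complete-case result whatever the dropout pattern, and that agreement could be misread as robustness.

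**Working it through.** **1. How many are affected**

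The inputs are in Protocol D.3.1.

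- Plan's own figure: 416 of 536 is 77.6%, so 536 − 416 = 120 are missing (22.4%).
- At the stated 25%: 536 × 0.25 = 134 missing, leaving 402.

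The stated 416 is 14 above 402, but both inputs are given as approximate. The range is 120 to 134.

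**2. What the ANCOVA uses**

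The model is 6-month outcome = arm + baseline covariates. A participant enters only with a 6-month value. Interim use and urine are not in the model, so they contribute nothing for a dropout.

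**3. What that could do to the estimate**

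The documents give no attrition by arm and no predictors of dropout, so every mechanism here is an assumption. The simulated trial has 536 participants, 1:1, with T = 1 for BMI+SC:

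- baseline b ~ N(0,1)
- Week 6 value w6 = 0.6b + 0.3T + 0.8e
- 6-month value y = 0.3b + 0.6·w6 + 0.02T + 0.66e′

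The total effect is 0.6 × 0.3 + 0.02 = 0.20, of which 0.18 passes through Week 6. Dropout follows logit P(missing) = intercept − slope × w6. There were 4,000 trials per scenario (Monte Carlo standard error 0.0013), using arm-specific regression imputation and point estimates only.

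| Dropout mechanism (slope) | Complete-case | Imputed, baseline only | Imputed, baseline + Week 6 |
|---|---|---|---|
| Random, 22.4% | 0.200 | 0.200 | 0.201 |
| Equal in both arms (0.9) | 0.186 | 0.186 | 0.199 |
| Twice as steep in SC (0.6 v 0.3) | 0.171 | 0.171 | 0.200 |
| Twice as steep in BMI+SC (0.6 v 0.3) | 0.218 | 0.219 | 0.198 |
| SC only, moderate (0.6) | 0.144 | 0.143 | 0.200 |
| SC only, strong (1.2) | 0.114 | 0.111 | 0.202 |
| BMI+SC only, moderate (0.6) | 0.246 | 0.247 | 0.197 |
| BMI+SC only, strong (1.2) | 0.270 | 0.272 | 0.200 |

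Reruns with new seeds agreed within about 0.005. Overall loss was not held fixed in the one-arm rows. Recalibrated to 22.4% in each arm, complete-case gives 0.154 and 0.115 (SC only) and 0.249 and 0.288 (BMI+SC only).

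The standard error of one trial's estimate is about 0.08. The bias is therefore:

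- equal dependence: 0.014/0.08 ≈ 0.2 standard errors
- twofold difference, SC steeper: 0.029/0.08 ≈ 0.4
- strong SC-only: 0.086/0.08 ≈ 1.1

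With no true effect, a separate 2,000-trial run rejected in 5.2% of trials under equal dependence and 7.2% with SC twice as steep.

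**4. How much interim data the dropouts must hold**

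In the strong SC-only case, imputation gives 0.202 if all dropouts have Week 6 data, 0.164 if half lack it and 0.111 if all lack it. If they hold Week 2 data alone, it gives 0.122 to 0.167 for Week 2/Week 6 residual correlations of 0.4 to 0.8.

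**5. Urine screen, if analysed at 6 months**

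D.7.1 says: "In a likely scenario of 50% positive urine screens, we are adequately powered (.80) to detect a 14% or more difference in rates". Taking 50% v 36% positive, a true difference of about −14.0 points, with 22.4% missing per arm and 1,500 trials per scenario, complete-case gives:

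- random: −13.9
- equal: −13.8
- twice as steep in SC or BMI+SC: −13.1 or −14.7
- SC only: −12.4 to −10.8
- BMI+SC only: −15.8 to −16.9

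Imputation with Week 6 use gives −13.8 to −14.2. Interim urine results and service-contact records were not simulated.

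**6. Dropout driven by the unseen 6-month value in one arm (slope 1.2)**

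Both methods are biased: complete-case 0.048 or 0.333; imputation with Week 6 use 0.094 or 0.292.

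**The case against.** The other side has a fair case, and most of it limits the point without removing it.

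- **A reader might infer that the 6-month result will be biased.** The documents do not support that. They point to no dropout mechanism. Assessment number, compensation and locator procedures are common to both arms (Protocol D.4.4, D.4.5), and the large figures need dependence in one arm and none in the other.
- **A reader might infer that the planned imputation is baseline-only.** The SAP does not say so. The covariate list in D.7 belongs to the outcome models. The gap is an unspecified imputation, not a wrong one.
- **A reader might take the 6-month urine regression as stated.** The logistic sentence gives no time point. Six months is inferred from the preceding sentence and from the urine indicator in the structural equation model; D.5.1 calls the urine analysis secondary.
- **A reader might see a power shortfall here.** The 416 is already net of attrition, so the issue is possible bias and unused data.
- **The growth curves use all six time points.** They do, but they are exploratory and test time by condition, so they do not change how the ANCOVA handles dropout.
- **The benefit of imputation is itself assumed.** This stands. The simulation sends 90% of the effect through Week 6 (0.18 of 0.20), and the documents do not say how many dropouts will hold interim data.

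What remains is that the retention claim fails for this model, and that the SAP relegates to a sensitivity analysis, without specification, a method it describes as less biased than most alternatives.

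**Conclusion.** The point holds in a limited form and is worth considering rather than critical. For the 6-month abstinence ANCOVA, and for the urine regression if it is run at 6 months, the main analysis is complete-case. It omits 120 to 134 participants and any interim data held for them. The direction and size of bias cannot be known from the documents. Under the assumed mechanisms it is nil with random dropout, small with equal dependence and modest with a twofold difference between arms; it is comparable to a standard error only in the one-arm extremes. Imputing with Week 6 use recovered 0.197 to 0.202 at no loss of precision, provided dropouts had that value and their 6-month outcome was missing at random. Imputing from baseline alone stayed within 0.003 of complete-case throughout. The structural equation model and the records-based recidivism analysis are outside this point.

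**What to change.** For these analyses, amend SAP D.7.1 as follows:

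- Make the multiple imputation already planned the main analysis, done separately by arm.
- Name its variables: Week 2, 4 and 6 substance use and urine results, the ANCOVA covariates, affective psychopathy group and service-contact records.
- Use the post-randomisation variables in the imputation model only, not as covariates in the ANCOVA or logistic model.
- Keep pairwise deletion as the sensitivity analysis, and remove the claim of full retention for these models.
- State the time point of the urine regression.

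Optionally, add a delta-shift analysis, applied in each arm in turn, for data missing not at random. A shift in one arm moves the estimate by missing fraction × delta, so removing an effect of 0.20 would take 0.20/0.25 = 0.80 to 0.20/0.224 = 0.89.

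The cost is SAP wording and no new data collection. The downside is that the main result then relies on missing-at-random and on the imputation model, and little is gained if most dropouts also lack interim data. At the least, naming the interim variables in the existing sensitivity imputation would let it detect dropout related to early use where those data are held.
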